Five open-label safety, tolerability and Phase 2 studies of ecopipam in 56 subjects with schizophrenia were conducted. Subjects diagnosed with acute schizophrenia, schizophreniform disorder, or bipolar schizoaffective disorders were treated with ecopipam HCl up to a daily dose of 600 mg. The maximum duration of treatment was six weeks. Ecopipam, when administered to subjects with schizophrenia, did not demonstrate efficacy in these studies. The most commonly reported adverse events were somnolence (21%, 12/56), headache, nausea, vomiting and dizziness (each reported in 14%, 8/56 subjects), insomnia (9%, 5/56), dyspepsia (7%, 4/56), and anxiety (7%, 4/56).

In a Phase 2, double-blind, placebo-controlled study (C/I98-271), 185 subjects with a primary diagnosis of moderate to severe obesity were treated with ecopipam HCl (10, 30, or 100 mg PO, once per day) for 12 weeks. Subjects receiving ecopipam HCl showed a dose-dependent weight loss. The most commonly reported adverse events by subjects receiving ecopipam HCl were headache, 19% (36/185), viral infection, 19% (36/185), somnolence, 18% (34/185), insomnia, 9% (17/185), and nausea, 9% (16/185).

In three Phase 3, double-blind, placebo-controlled studies (P00359, P00396, and P00741), obese subjects including type 2 diabetic subjects were treated with ecopipam HCl (50 or 100 mg PO, QD) for 52 weeks. Subjects receiving ecopipam HCl showed a dose-dependent weight loss. These Phase 3 studies were discontinued because of unexpected psychiatric adverse events (ecopipam 31% vs. placebo 15%), including depression, anxiety, and suicidal ideation, thereby excluding its projected use in weight management. The most frequently reported adverse events in all Phase 3 obesity studies receiving ecopipam HCl were upper respiratory tract infection, 30% (439 of 1482 subjects reporting), insomnia 17% (248/1482), headache, 16% (244/1482), depression, 16% (236/1482), somnolence, 15% (216/1482), fatigue, 15% (215/1482), anxiety, 14% (211/1482), pharyngitis, 9% (137/1482), back pain, 8% (114/1482), nausea, 7% (107/1482). The frequencies of insomnia, depression, somnolence and anxiety were about twice as frequent in subjects receiving ecopipam HCl compared to placebo. The frequencies of upper respiratory

tract infection, headache, fatigue, pharyngitis, back pain and nausea were similar in frequencies in subjects receiving ecopipam and placebo.

Clinical Summary: Legacy Psyadon Studies in Indications other than TS

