8.3. Subject Withdrawal, Removal, and Replacement Criteria

Any subject with a CDRS-R assessment indicative of the onset of a new depressive episode at any visit can be discontinued from study participation at the discretion of the Investigator. Any subject with a new positive response on questions 4 and/or 5 of the C-SSRS will be immediately discontinued and evaluated for risk. Dosing may be restarted at the discretion of the Investigator following consultation with the Sponsor or its designee.

The Investigator or subject may choose to stop study treatment at any time for safety or personal reasons.

Where possible, a subject who discontinues treatment will undergo protocol-specified end-of study procedures at the time of discontinuation. Date and reason(s) of premature discontinuation will be described in the CRF. In addition, the date of last dose of study treatment will be recorded on the Study Treatment Dosing CRF.

Subjects who discontinue treatment for any reason, other than an SAE (even if the SAE is not treatment related) or an AE (unless the AE can be determined to be unrelated to treatment), may be replaced only after consultation with Sponsor or its representative.

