3.5. Determination of Sample Size

A sample size of 75 subjects per group will provide >80% power to detect difference between groups of 3 points on change from baseline the Yale Global Tic Severity Scale-Total Tic Score (YGTSS-TTS), with standard deviation = 6.1 and alpha = 0.05, assuming 10% drop out.

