3.6. Treatment Assignment & Blinding

Subjects will be randomized 1:1 to either ecopipam or matching placebo. Randomization will be stratified by weight band (\geq 18 to \leq 23 kg, >23 to \leq 34 kg, >34 to \leq 44 kg, >44 to \leq 68 kg, >68 to \leq 83 kg, >83 kg).

Throughout the study, subjects and all personnel involved with the conduct and interpretation of the study, including the subject, parents/guardians, investigators, site personnel, and sponsor staff will be blinded to the treatment codes. Randomization data will be kept strictly confidential, filed securely by an appropriate group with the Sponsor or Syneos and accessible only to authorized persons (e.g., Safety) until the time of unblinding.

A master list of all treatments and the subject numbers associated with them will be maintained electronically by the unblinded clinical supply vendor and the unblinded personnel at Syneos. The process to request unblinding and the randomization code will be outlined in a separate document. The site will be trained in this process and it should be used only in an emergency. These codes should only be broken if knowledge of the subject's randomization code will affect his/her medical treatment. If possible, before breaking the blind, the Investigator should consult with the Sponsor to ascertain the necessity of breaking the code. The Investigator is to record the date and time of requesting the code and the reason for breaking the code.

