10.9.5. Children's Depression Rating Scale-Revised (CDRS-R)

Children's Depression Rating Scale-Revised (CDRS-R) is a clinically validated rating scale designed to assess psychiatric signs and symptoms of depressions. Fourteen signs and symptoms are rated from 1 (normal) to 7 (most severe), and 3 signs and symptoms are rated from 1 (normal) to 5 (most severe). The raw summary score is the sum of all 17 items, ranging from 17 to 113.

The raw summary score will be summarized by treatment group at the Baseline, Week 4, Week 6, Week 8 and Week 12 visits and all questionnaire data will be displayed in a listing.

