10.10. COVID-19 Analyses

Due to COVID-19 pandemic, additional analyses will be conducted:

- Listings of COVID-19 related study disruptions by subject and by site, including descriptions of the disruption.
- The amount of missing data by treatment group and overall by endpoint for data missing due to COVID-19 will be summarized in a table.
- Protocol deviations due to COVID-19 will be summarized by type and treatment in a table.

11. Interim Analyses

An unblinded interim analysis will be conducted when approximately 50% of the 150 planned subjects have been randomized (1:1 ratio between ecopipam and placebo) and completed treatment or are terminated early. The interim analysis will be performed by an independent statistician and governed by an external Data Safety Monitoring Board (DSMB). The conditional power will be calculated to help the DSMB assess the probability of a successful study based on observed data.

The primary efficacy endpoint of the study is the YGTSS-TTS. A smaller YGTSS-TTS score indicates a better condition in subjects with Tourette's syndrome, and we may expect that the ecopipam group has a larger reduction than the placebo group. Let μ_{σ} be the mean change YGTSS-TTS score from Baseline to Week 12 for the ecopipam group, and μ_p be the mean change YGTSS-TTS score from Baseline to Week 12 for the placebo group. Then, given $H_0: \mu_{\sigma} \ge \mu_p \equiv \Delta_{\sigma-p} \ge 0$ vs. $H_1: \mu_{\sigma} < \mu_p \equiv \Delta_{\sigma-p} < 0$. Since the original sample size calculation is based on two-sided test at a significance level of α =5%, we will use $\alpha/2$ =2.5% to match the one-sided test.

The primary endpoint will be analyzed with a Mixed Model for Repeated Measures (MMRM) model using the SAS MIXED procedure with REPEATED statement. The model will include fixed effects for treatment, visit, visit interaction between treatment and visit, region, age group (0 = children 6-11, 1 = adolescents 12-17) and covariate for baseline YGTSS-TTS.

To determine if the total sample size should be increased from N (to N^*), the conditional power based on the MMRM will be calculated at the interim analysis using the observed effects (where n=75) and the planned sample size (N=150).

If it is determined that the sample size should be increased, the CHW (Cui-Hung-Wang) statistic, which controls the type I error, will be used. The CHW statistic is a weighted statistic defined as:

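### CDRS-R is summarised only as raw scores by arm and scheduled visit, so a child's worsening from Baseline appears only in listings unless it is also recorded as an adverse event

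*SAP*

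**What the plan says.** SAP 10.9.5 defines the CDRS-R raw summary score (17 items, range 17 to 113) and plans: "The raw summary score will be summarized by treatment group at the Baseline, Week 4, Week 6, Week 8 and Week 12 visits". All questionnaire data are also listed. Under SAP 6.1 a continuous summary gives n, mean, SD, median, minimum and maximum. By-visit summaries use the nominal visit, and unscheduled visits are listed but not summarised. SAP 6.4 uses no visit windows.

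Protocol 5.3.3 names the depression scale among those used to assess possible worsening of psychiatric symptoms. Protocol 8.3 goes further and leaves the decision to the investigator: "Any subject with a CDRS-R assessment indicative of the onset of a new depressive episode at any visit can be discontinued from study participation". It states no score or change that defines such an episode. It asks for end-of-study procedures at discontinuation where possible, and the Schedule of Assessments puts CDRS-R in the combined Completion/Early Termination column.

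On background risk, Protocol 5.2.2.1 says of the adult obesity programme: "These Phase 3 studies were discontinued because of unexpected psychiatric adverse events (ecopipam 31% vs. placebo 15%), including depression, anxiety, and suicidal ideation". Depression was reported in 16% (236/1482) on ecopipam, about twice the placebo frequency.

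**The concern.** Worsening and onset of an episode are changes within a child. A raw-score summary by arm and visit does not show them: a child who starts low and rises sharply contributes one value among many, and the table does not link that value to the child's own Baseline. A child discontinued under Protocol 8.3 gives no later scheduled scores, so later visit summaries describe those who stayed. The score taken at early termination has no stated place in the summary.

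What is at stake is whether a reader of the study report can see, by arm, how many children worsened on the scale and by how much. Psychiatric adverse events, depression among them, stopped the adult Phase 3 studies, so the question will be asked.

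**Working it through.** **1. The plan's own sizing figure.** The documents size only the primary endpoint: "A sample size of 75 subjects per group will provide >80% power to detect difference between groups of 3 points", "with standard deviation = 6.1 and alpha = 0.05, assuming 10% drop out", with 1:1 allocation and a two-sided 5% test (SAP 3.5, 3.6, 11). n per arm = 2 × 6.1² × (1.96 + 0.84)² / 3² gives 65. With 10% dropout, 65 / 0.9 gives 73, close to the stated 75. Power at 75 × 0.9 = 67.5 per arm is about 81.5%. The figure reproduces. It says nothing about CDRS-R; it only supplies the arm size used below.

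**2. How the SAP summarises other safety measures.**

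| Measure | Section | Change from Baseline | Category or count of subjects |
|---|---|---|---|
| Laboratory | 10.4 | yes | shift tables |
| Weight | 10.5 | yes | gain of 7% or more |
| ECG | 10.6 | yes | overall result (normal/abnormal) |
| C-SSRS | 10.8 | no | number and percent |
| CDRS-R | 10.9.5 | no | none |
| PARS | 10.9.6 | no | none |

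**3. Where a worsening child would appear.**
- Score at a scheduled visit: in that visit's raw summary, not as a change.
- Score at an unscheduled visit: listing only (SAP 6.1).
- Score at early termination: placement unstated.
- Recorded as an adverse event: in the Depression and Suicide/Self Injury special-interest table (SAP 10.3).
- Recorded as leading to discontinuation: in the AE-termination table (SAP 10.3) and the disposition table (SAP 7.1).

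Adverse events come from spontaneous report, open questions or observation (Protocol 12.4). Protocol 12.1.3 expressly requires signs of abuse, withdrawal or dependence to be recorded as adverse events; no matching sentence covers a CDRS-R finding. The discontinuation reasons in Protocol 7.5 have no depression category.

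**4. Illustration of what the visit means would show.** From the documents: 16% on ecopipam and, by halving, about 8% on placebo. Assumed, not in the documents: an episode raises CDRS-R by 20 to 40 points, and the SD among other children is 8 to 12. With 75 per arm and every affected child still assessed:
- Difference in means = (0.16 − 0.08) × rise = 1.6 to 3.2 points.
- Variance in an arm = SD² + p(1 − p) × rise². For rise 20 and SD 8: 64 + 53.76 = 117.76 and 64 + 29.44 = 93.44. SE = √((117.76 + 93.44) / 75) = 1.68, and 1.6 / 1.68 = 0.95.
- Over the whole range the ratio is 0.7 to 1.3 standard errors.

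If half the affected children have left, the remaining proportions are 0.08 / 0.92 = 0.087 and 0.04 / 0.96 = 0.042. The difference is then 0.9 to 1.8 points (0.4 to 0.9 standard errors). If all have left, it is 0.

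**5. The same rates as counts.** 75 × 0.16 = 12 and 75 × 0.08 = 6. Power of a two-sided 5% test, with the pooled SE under the null: Φ((0.08 − 1.96 × 0.0531) / 0.0527) = Φ(−0.456) = 32%. With Fisher's exact test it is 25%. So the counts would not settle the question either. Their value is to show how many children were affected.

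**The case against.** The strongest reply is that the plan already counts depression. It is a pre-specified special-interest event with its own by-arm table, AEs leading to termination and reasons for discontinuation are tabulated, and C-SSRS is reported as number and percent. Protocol 12.2.1.1 defines an adverse event as the development of an undesirable medical condition and requires all to be recorded, so a new depressive episode should be captured. The 16% is itself an adverse-event frequency, so the like-for-like comparison is the adverse-event table. This stands, and it narrows the gap to two things: scale-detected episodes that nobody records as an adverse event, and worsening short of an episode.

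It also stands that the minimum and maximum are planned, that a score prompting discontinuation at a scheduled visit is already in that visit's summary, that discontinuation under 8.3 is discretionary, and that Protocol 13.2.2 intends these scales to be descriptive. The adult rates come from 52-week obesity studies. This is a 12-week paediatric trial that excludes a major depressive episode in the past 2 years, and the earlier paediatric crossover study saw no evidence of an effect on CDI scores.

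A reader might infer more: that affected children vanish from the whole report, that CDRS-R is the trial's principal measure of this harm, or that depression alone ended Phase 3. The documents support none of these. The adverse-event tables and the listing remain, the SAP places CDRS-R under Other Safety, and the Phase 3 studies stopped for psychiatric events that also included anxiety and suicidal ideation.

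What the reply does not meet is that the protocol uses the scale to find within-child worsening, while the SAP tabulates no within-child quantity for it.

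**Conclusion.** The gap is real and limited. CDRS-R is reported as raw-score descriptive statistics at nominal visits, without change from Baseline or a worst value, and early-termination scores are unassigned. Within-child worsening on the scale therefore appears only in listings unless it is also recorded as an adverse event.

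The size given (1.6 to 3.2 points, 0.7 to 1.3 standard errors, or about 12 against 6 children) is illustrative. It rests on adult 52-week rates, an inferred placebo rate, and assumed rises and SDs. It shows that a doubling of episodes could pass unnoticed in the visit means; it does not predict this trial. The case rests on matching the summary to the protocol's use of the scale, not on power. It is a cheap improvement to safety reporting and does not touch the efficacy conclusions.

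**What to change.** In SAP 10.9.5, keep the by-visit raw summaries and add by arm:

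1. Change from Baseline at each visit.
2. Each subject's worst post-baseline change from Baseline (n, mean, SD, median, range and cumulative distribution), using all scheduled, unscheduled and early-termination scores. State where early-termination scores go in the by-visit table.
3. A descriptive count of subjects whom the investigator judged under Protocol 8.3 to have a CDRS-R-indicated new depressive episode, cross-tabulated with the Depression special-interest events.

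Protocol 8.3 gives no cut-off, so any numeric criterion must come from the sponsor; none is proposed here. The sponsor should also confirm that the judgement is recorded for children who stay in the study, since 8.3 asks for reasons only at discontinuation.

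In SAP 10.9.6 add items 1 and 2 for PARS. Item 3 does not apply there, because 8.3 has no PARS rule.

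Items 1 and 2 cost SAP wording and one or two descriptive tables from data already collected. Item 3 adds a small table and depends on that judgement being recorded. No visit, dose, test or alpha changes.

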10.9.6. Pediatric Anxiety Rating Scale (PARS)

Pediatric Anxiety Rating Scale (PARS) is a clinician-rated instrument for assessing the severity of anxiety symptoms associated with common anxiety disorders and generalized anxiety in children and adolescents. The PARS has two sections: the symptom checklist and the severity items. The symptom checklist is used to determine the child's repertoire of symptoms during the past week. The 7-severity item is used to determine severity of symptoms and the PARS total score. Each severity item is coded from zero (none) to 5 (most extreme). Not applicable is coded to 8, and does not know is coded to 9. The total score for the PARS is total of the 7 severity items. The total score ranges from 0 to 35. Codes "8" and "9" are not included in the summation.

The total score will be summarized by treatment group at the Baseline, Week 4, Week 6, Week 8 and Week 12 visits and all questionnaire data will be displayed in a listing.

10.10. COVID-19 Analyses

Due to COVID-19 pandemic, additional analyses will be conducted:

- Listings of COVID-19 related study disruptions by subject and by site, including descriptions of the disruption.
- The amount of missing data by treatment group and overall by endpoint for data missing due to COVID-19 will be summarized in a table.
- Protocol deviations due to COVID-19 will be summarized by type and treatment in a table.

11. Interim Analyses

An unblinded interim analysis will be conducted when approximately 50% of the 150 planned subjects have been randomized (1:1 ratio between ecopipam and placebo) and completed treatment or are terminated early. The interim analysis will be performed by an independent statistician and governed by an external Data Safety Monitoring Board (DSMB). The conditional power will be calculated to help the DSMB assess the probability of a successful study based on observed data.

The primary efficacy endpoint of the study is the YGTSS-TTS. A smaller YGTSS-TTS score indicates a better condition in subjects with Tourette's syndrome, and we may expect that the ecopipam group has a larger reduction than the placebo group. Let μ_{σ} be the mean change YGTSS-TTS score from Baseline to Week 12 for the ecopipam group, and μ_p be the mean change YGTSS-TTS score from Baseline to Week 12 for the placebo group. Then, given $H_0: \mu_{\sigma} \ge \mu_p \equiv \Delta_{\sigma-p} \ge 0$ vs. $H_1: \mu_{\sigma} < \mu_p \equiv \Delta_{\sigma-p} < 0$. Since the original sample size calculation is based on two-sided test at a significance level of α =5%, we will use $\alpha/2$ =2.5% to match the one-sided test.

The primary endpoint will be analyzed with a Mixed Model for Repeated Measures (MMRM) model using the SAS MIXED procedure with REPEATED statement. The model will include fixed effects for treatment, visit, visit interaction between treatment and visit, region, age group (0 = children 6-11, 1 = adolescents 12-17) and covariate for baseline YGTSS-TTS.

To determine if the total sample size should be increased from N (to N^*), the conditional power based on the MMRM will be calculated at the interim analysis using the observed effects (where n=75) and the planned sample size (N=150).

If it is determined that the sample size should be increased, the CHW (Cui-Hung-Wang) statistic, which controls the type I error, will be used. The CHW statistic is a weighted statistic defined as:

$$T_{CHW} = \sqrt{\frac{n_1}{N}} T_1 + \sqrt{\frac{n_2}{N}} T_2^*$$

The validity of the CHW test statistic requires that pre-interim (Stage 1) and post-interim (Stage 2) statistics T_1 and T_2^* be stochastically independent of each other. Under the various scenarios described below, the T_1 statistic will be based the least-square means from the Stage 1 MMRM model. Specifically, at Stage 1 the mean difference Δ_{e-p} (treatment effect of ecopipam versus placebo) is the difference in least-square means of change from baseline at Week 12 from the MMRM. The LSMEANS statement with COV option will report the covariance of LS means and the variance $var(\delta_1)$ of the difference can be calculated. Thereby, the t-statistic T_1 at the interim analysis can be calculated as:

$$T_1 = \frac{\delta_1}{\sqrt{var(\delta_1)}}$$
, where $\delta_1 = LSM_e - LSM_p$

The T_2^* statistic will be defined in two ways to produce three conditional power calculations, as follows:

Firstly, T_2^* will be based on Stage 2 sample means assuming all Stage 2 subjects complete the Week 12 assessment. Then the Stage 2 (post-interim analysis) t-statistic T_2^* at the interim analysis can be calculated as:

$$T_2^* = \frac{\widehat{\delta}_2}{\sigma \sqrt{2/k_2^*}}$$
where $\hat{\delta}_2$ is the observed treatment mean difference in the change of YGTSS-TTS from baseline to Week 12 when the k_2^* subjects in Stage 2 complete Week 12 of study for each group.

Given the information at Stage 1,

$$E(T_{CHW}|T_1) = \sqrt{\frac{n_1}{N}}T_1 + \sqrt{\frac{n_2}{N}}\frac{\delta}{\sigma\sqrt{2/k_2^*}} = \sqrt{\frac{n_1}{N}}T_1 + \sqrt{\frac{n_2k_2^*}{2N}}\frac{\delta}{\sigma}$$
$$Var(T_{CHW}|T_1) = \frac{n_2}{N}var(T_2^*) = \frac{n_2}{N}$$

Thus, the conditional power is:

$$CP = P(T_{CHW} < -Z_{\alpha/2} | T_1) \approx 1 - \Phi(\sqrt{\frac{N}{n_2}} Z_{\alpha/2} + \sqrt{\frac{n_1}{n_2}} T_1 + \sqrt{\frac{k_2^*}{2}} \frac{\delta}{\sigma})$$

The condition power will then be calculated under the following scenarios for the treatment difference δ and standard deviation σ :

- 1) Using the values hypothesized in the protocol. Treatment difference $\delta = 3$ and standard deviation $\sigma = 6.1$
- 2) Using the estimates from the Stage 1 data. Treatment difference δ is the Stage 1 observed sample mean difference in change from baseline between the two treatment groups, and standard deviation σ is the pooled standard deviation of the change from baseline, both based on the completers in the respective treatment groups.

If the drop-out rate based on the first stage is f, the corresponding sample size at 2^{nd} stage should be $n_2^* = k_2^*/(1-f)$, and the new total sample size is $N^* = n_1 + n_2^*$.

Secondly, T_2^* will be based on Stage 2 least-squares mean difference assuming all Stage 2 subjects will have the same trend in treatment difference and variability, as does Stage 1. The treatment difference \bar{o} will be estimated by the least-squares means difference between treatments observed in Stage 1. As above, define $T_2^* = \frac{\hat{\delta}_2}{\sqrt{var(\hat{\delta}_2)}}$, where $\hat{\delta}_2$ is the future estimate of treatment effect from Stage 2. The inequality $T_{aver} \leq -\overline{Z}_{-v}$ is can be written as:

inequality $T_{CHW} < -Z_{\alpha/2}$ can be written as:

$$\frac{\hat{\delta}_2 - \delta}{\sqrt{var(\hat{\delta}_2)}} < \sqrt{\frac{N}{n_2}} \left(-Z_{\alpha/2} - \sqrt{\frac{n_1}{N}}T_1 \right) - \frac{\delta}{\sqrt{var(\hat{\delta}_2)}}$$

As above, n_1 , n_2 , N, and T_1 are known at the time of the interim analysis, and the treatment effect, δ , is hypothesized as that estimated in Stage 1. The remaining term, $var(\hat{\delta}_2)$, is estimated as:

$$var(\hat{\delta}_2) = n_1 Var(\hat{\delta}_1)/k_2^*$$

To justify this equation, note that the variance of an MMRM estimate of treatment effect depends on sample size, other aspects of study design incorporated in the model (e.g., covariate, stratification factors, etc.), and underlying population variability. Define D to be the component of $var(\hat{\delta}_1)$ that incorporates all design and covariate features but sample size, i.e., $var(\hat{\delta}_1) = \frac{D}{n_1}$, so that $D = n_1 var(\hat{\delta}_1)$. Assuming that the model components and underlying population variability in Stage 2 are the same as in Stage 1, we have $var(\hat{\delta}_2) = \frac{D}{k^4}$.

It follows that $var(\hat{\delta}_2) = n_1 Var(\hat{\delta}_1)/k_2^*$. Therefore, the conditional power is:

$$CP = \Phi\left(\sqrt{\frac{N}{n_2}} \left[-Z_{\alpha/2} - \sqrt{\frac{n_1}{N}} T_1 \right] - \frac{\delta}{\sqrt{n_1 Var(\hat{\delta}_1)/k_2^*}} \right)$$

The condition power will then be calculated under the following for the treatment difference δ and standard error $Var(\hat{\delta}_1)$:

3) Using the estimates from the stage 1 data. Treatment difference δ is the Stage 1 MMRM treatment effect (δ₁) and Var(δ₁) is the variance of this estimate of treatment difference based on the covariance matrix of the LSmeans.

Using these results, the DSMB may make one of the following recommendations:

- If the conditional power at the planned sample size (150) is less than 30% then the DSMB may recommend that the study be terminated for futility.
- 2) If the conditional power at the planned sample size (150) is greater than 30% and less than 80%, then the planned sample size will be increased up to 200 to try to achieve a conditional power of at least 80%. If the conditional power at the maximum sample size (200) is still less than 80%, the DSMB may recommend continuing the study at the maximum sample size (200).
- If the conditional power is at least 80%, then the DSMB may recommend continuing this study with the planned sample size (150).

Full details of the DSMB including primary responsibilities, its relationship with other study components, its membership, and the purpose and timings of its meetings are documented in a DSMB charter. These details will also include procedures to ensure confidentiality and proper communication, the guidelines to be implemented by the DSMB and an outline of the content of the closed reports (unblinded) and open reports (blinded) that will be provided to the DSMB.

12. Changes from Analysis Planned in Protocol

There are no changes from the analysis planned in protocol.

13. Reference List

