T_{CHW} will be compared to a standard Gaussian distribution to determine the level of statistical significance. Here n₁ is the **actual** number of subjects in Stage 1 (planned to be 75 subjects), n₂ is the **planned** number of Stage 2 subjects before any sample size increase (i.e., 150 minus the actual number in Stage 1), N is the sum of n₁ and n₂ (i.e., 150), and T₁ and T₂ are the t-statistics for treatment difference from MMRM models on data from, respectively, Stage 1 and Stage 2 data. At a given stage, the mean difference Δ_{e-p} (treatment effect of ecopipam versus placebo) can be estimated by the difference $\hat{\delta} = LSM_e - LSM_p$ in least squares (LS) means of change from baseline at Week 12 between the ecopipam and placebo treatment groups, respectively. The LSMEANS statement with COV option will report the estimated covariance of LS means, which can be used to derive the variance $v \hat{ar}(\hat{\delta})$ of the difference $\hat{\delta}$. The t-statistic T₁ or T₂ can then be calculated as:

$$T = \frac{\widehat{\delta}}{\sqrt{\widehat{var}(\widehat{\delta})}}$$

If the planned sample size is adjusted and the CHW method used to analyze the primary endpoint, the MMRM model and sensitivity analyses of the complete dataset as if the sample size had been planned from the beginning will be performed to provide complementary interpretation to the CHW analysis.

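### The conditional power formulas in SAP section 11 contain a sign error and use one symbol, k2*, on incompatible scales, so they cannot all be correct as printed

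*SAP*

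**What the plan says.** SAP section 11 expects a fall in the score: "we may expect that the ecopipam group has a larger reduction than the placebo group". The alternative hypothesis is that ecopipam minus placebo is below zero. The Stage 1 estimate follows the same direction ("where $\delta_1 = LSM_e - LSM_p"), and conditional power is the probability of the lower tail ("CP = P(T_{CHW} < -Z_{\alpha/2} | T_1").

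Three conditional powers follow.

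- **Scenario 1** uses the protocol assumptions: "Treatment difference $\delta = 3$ and standard deviation $\sigma = 6.1".
- **Scenario 2** uses the Stage 1 completers' mean difference and pooled SD.
- **Scenario 3** uses the Stage 1 MMRM estimate and its variance.

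For scenarios 1 and 2 the Stage 2 statistic is set up "assuming all Stage 2 subjects complete the Week 12 assessment", with standard error `sigma*sqrt(2/k2*)`. There `k2*` is the number for whom "subjects in Stage 2 complete Week 12 of study for each group". The section then sets `n2* = k2*/(1-f)` and `N* = n1 + n2*`. For scenario 3 it sets `var(delta2) = n1*Var(delta1)/k2*`.

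SAP 8.1.1 defines `n1` as the actual "number of subjects in Stage 1 (planned to be 75 subjects"), out of 150 in both arms. Section 11 counts subjects who "have been randomized (1:1 ratio between ecopipam and placebo) and completed treatment or are terminated early", so `n1` is not limited to completers.

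The decision rules at the end of section 11 apply 30% and 80% to the conditional power at 150 subjects and cap any increase at 200. They do not say which of the three values is meant.

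**The concern.** There are three faults.

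1. **Sign.** With a lower-tail test and an effect defined as ecopipam minus placebo, a benefit of 3 points has to enter as -3. Entering +3 calculates the chance of success if the drug is 3 points worse than placebo.
2. **Scale of `k2*`.** It is per group in the scenario 1 and 2 formula, but it is added to, or divided into, a two-arm count elsewhere. It is also a count of completers, whereas `n1` is a count of subjects enrolled.
3. **Governing value.** Three conditional powers are produced and the decision rules name none of them.

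These values inform the recommendation to stop for futility, stay at 150 or grow to as many as 200. A literal program could show almost no chance of success for a trial that is on track, print a re-sized total below the planned 150, or place the trial in the wrong decision zone.

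**Working it through.** **Inputs.** Difference 3, SD 6.1, two-sided alpha 0.05, 75 per group and 10% dropout (SAP 3.5). `n1 = n2 = 75`, `N = 150`, both arms together (SAP 8.1.1 and 11). Limits 30% and 80%, cap 200 (SAP 11). Write `U = |T1|` for a Stage 1 result in favour of ecopipam; `sqrt(N/n2)*1.96 = 2.772`.

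**The plan's own figure.** With 67.5 completers per group, `3/(6.1*sqrt(2/67.5)) = 2.857`, so power is `Phi(2.857 - 1.96) = 81.5%`. The stated >80% reproduces. At half the information the expected T1 is `-2.857/sqrt(2) = -2.020`.

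**Sign (scenario 1).** The printed form is `CP = 1 - Phi(2.772 + T1 + sqrt(k2*/2)*delta/6.1)`. With `k2* = 37.5` per group, `sqrt(18.75)*3/6.1 = 2.130`. At T1 = -2.0:

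- delta = +3: `1 - Phi(2.902) = 0.2%`
- delta = -3: `1 - Phi(-1.358) = 91%`

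With 33.75 completers per group the values are 0.3% and 89%.

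**Re-sized total.** Take a true total of 200: Stage 2 enrols 125, or 56.25 completers per group at f = 10%. The printed formula gives `75 + 56.25/0.9 = 137.5`; the correct one gives `75 + 2*56.25/0.9 = 200`.

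To reach 80% conditional power, Stage 2 must be multiplied by `R = ((0.842 + 2.772 - U)/U)^2`. At U = 1.6, R = 1.584. The correct total is `75 + 75R = 194`; scenario 2 with per-group `k2*` prints `75 + 37.5R = 134`. This assumes that the completers' estimates give the same T1 as the MMRM.

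**Scenario 3.** Substituting `delta = delta1` gives `CP = Phi(-2.772 + U + U*sqrt(k2*/75))`. The table gives the U at which this reaches 30% and 80% with 150 subjects. It also gives the share of trials at the planned effect (T1 normal, mean -2.020, SD 1) that fall in a different zone from the enrolment basis.

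| Meaning of `k2*` | Value | U at 30% / 80% | Zone changed |
|---|---|---|---|
| Total enrolled (same basis as `n1`) | 75 | 1.12 / 1.81 | reference |
| Total completers, 10% dropout | 67.5 | 1.15 / 1.85 | about 2.7% |
| Per group, no dropout | 37.5 | 1.32 / 2.12 | about 18% (5.6% futility instead of enlarge, 12.3% enlarge instead of stay) |
| Per-group completers, 10% dropout | 33.75 | 1.35 / 2.16 | about 21% (6.5% and 14.1%) |

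For example, with `k2* = 37.5`, T1 = -1.25 gives 26% instead of 39%, and T1 = -2.0 gives 74% instead of 89%.

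**Can one meaning serve throughout?**

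- *Per group:* scenarios 1 and 2 are right at N = 150 once the sign is corrected. `N*` loses one Stage 2 arm, and scenario 3 uses about twice the right variance.
- *Total completers:* `N*` is right and scenario 3 is slightly low (63.5% instead of 66.6% at T1 = -1.6). The `sqrt(k2*/2)` term is too large in scenarios 1 and 2; scenario 2's limits fall from 1.12 / 1.81 to 0.93 / 1.50.
- *Total enrolled:* scenario 3 is right and the `sqrt(k2*/2)` term is again too large. `N*` also allows for dropout twice: at T1 = -1.6 it is `75 + 75*1.584/0.9 = 207` instead of 194 (200 at f = 5%, 215 at f = 15%). The cap of 200 limits this excess.

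**Which conditional power.** With signs and units corrected and no dropout, T1 = -1.0 gives 64% in scenario 1 (enlarge) and 22% in scenario 3 (futility zone).

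**The case against.** The strongest reply concerns consequence rather than algebra.

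- **Scenario 3 has a natural reading.** Its justification divides one design constant by the sample size of each stage, which makes sense only if `k2*` is on the same basis as `n1`. Read that way its conditional power is right, and the 18% to 21% arises only if the per-group definition is carried over. This is fair. But the symbol is not redefined, and its only stated definition is per group.
- **The dropout conversion** stands before scenario 3 and may not have been meant for it. Then scenario 3 has no stated route from `k2*` to a total.
- **Scenario 1 may not decide anything.** Section 11 ties re-sizing to the MMRM and the observed effects, and a 0.2% beside about 89% from scenario 3 would be noticed. This limits the harm but does not correct the entry.
- **Without scenario 1, the choice matters less.** Corrected scenarios 2 and 3 agree when the completer and MMRM estimates agree. The DSMB charter, not available here, may name the governing value. Protocol 13.2.5 also brings in safety and other charter criteria, and the DSMB only may recommend stopping. So what moves is the conditional power zone, not necessarily the decision.
- **A character may have been lost in reading the PDF.** A minus sign or a factor of 2 could have dropped out, so the signed SAP should be checked. The scenario 3 variance is printed more than once in the same form, so a lost character is an unlikely explanation there.

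**Conclusion.** The concern holds, and the formulas must be corrected before they are programmed. The sign in scenario 1 is wrong under the section's own convention, turning about 91% into 0.2% for a trial on track. The re-sized total omits one Stage 2 arm under the stated definition of `k2*`. No single definition repairs all the formulas. The effect on scenario 3 depends on the reading: none if `k2*` is total enrolment, about 2.7% of trials in a different zone if total completers, and about 18% to 21% if per group. The unnamed governing value would by itself be only a missing detail.

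The figures assume 75 subjects at the interim split evenly between arms, a normal T1, the planned effect and SD, and the plan's 10% dropout where stated. Three things are unaffected: the type I error of the CHW test, whose weights are fixed; the >80% fixed-design power; and the scenario 2 conditional power at 150 with `k2*` per group.

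**What to change.** In SAP section 11:

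1. Enter `delta = -3` in scenario 1.
2. Define `k2*` once, as Stage 2 Week 12 completers per group.
3. Write `n2* = 2*k2*/(1-f)` and `N* = n1 + n2*`, with `n2*` the two-arm Stage 2 enrolment.
4. In scenario 3, write `var(delta2) = Var(delta1)*n1/n2*` and carry it into the conditional power formula. At 150 subjects `n2* = 75`, which gives the 1.12 / 1.81 limits.
5. Name the conditional power that governs the 30% limit and the one that governs the 80% limit and re-sizing. Scenario 3 for re-sizing follows from the section's own reference to the MMRM and observed effects. Check that the DSMB charter agrees.

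The cost is a few lines of SAP text, the matching change to the interim program and a check of the charter. It needs no extra patients and no change to the design, thresholds or CHW weights.
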